4.6.5.3 ECOG Performance Status

Performance status will be assessed using the ECOG scale. Descriptive statistics will be presented for observed values and changes from baseline at each visit where assessments were scheduled to be collected per the clinical study protocol. Results will be presented in patient data listings.

4.6.5.4 Prior and Concomitant Medications

Medications will be coded using the latest version of the World Health Organization Drug Dictionary Enhanced (WHODDE). Medications entered on the eCRF will be mapped to Anatomical Therapeutic Chemical (ATC) drug class (level 4) and drug name.

Prior and concomitant medications will be summarized separately, and the categorization of each medication will be determined programmatically based on medication start and end dates. A prior medication is defined as any medication administered prior to the date of the first dose of study drug with an end date prior to date of first dose of study drug. A concomitant medication is defined as any medication administered on or after the date of the first dose of study drug through 90 days after the last dose of study drugs. Any medication whose start date/time cannot be determined due to partial or missing medication start and/or end dates will be considered a concomitant medication.

For both prior and concomitant medications summaries, the number and percentage of patients receiving any medication will be summarized by cohort, as will the number and percentage receiving any medication by ATC drug class and generic drug name. Prior medications will also be summarized over all patients combined. Patients reporting use of more than one medication at each level of summarization (any medication received, ATC class, and generic drug name) will be counted only once. ATC class terms will be displayed by descending order of incidence, as will generic drug names within each ATC class. The study phase during which each medication was received (e.g., prior, concomitant, or both) will be presented on the listing of prior and concomitant medications.

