3.4.2 Safety Variables

3.4.2.1 Adverse Events

An AE is any untoward medical event that occurs to a patient following the start of administration of the study treatment, whether or not the event is considered study drug related. Any worsening (i.e., any clinically significant adverse change in the frequency or intensity of a pre-existing condition) should be considered an AE.

For all patients (excluding those in Phase 2 receiving nanatinostat, valganciclovir, and pembrolizumab), AEs will be recorded from the signing of the informed consent form (ICF) up to and including 30 days (90 days for SAEs) after the last dose of study treatment or until the start of subsequent anticancer therapy, whichever occurs first. For patients in Phase 2 who receive nanatinostat, valganciclovir, and pembrolizumab, AEs will be recorded from the signing of the ICF up to and including 90 days after the last dose of study treatment or until a new anticancer treatment is started, whichever is first.

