4.6.2 Adverse Events

Treatment-emergent adverse events (TEAEs) are defined as those AEs with onset after the first dose of study drug or existing events that worsened after the first dose during the study. Treatment-emergent AEs will be summarized by phase and treatment group. Events reported with a partial onset date (e.g., month and year are reported but the day

is missing) will be considered to be treatment-emergent if it cannot be confirmed that the event onset was prior to the first dose of study drug based on the available date entries.

Verbatim terms on case report forms will be mapped to preferred terms and system organ classes using MedDRA, version 27.1)

Summaries that are displayed by system organ class and preferred terms will be ordered by descending incidence of system organ class and preferred term within each system organ class. Summaries displayed by preferred term only will be ordered by descending incidence of preferred term. Summaries of the following types will be presented:

- Overall summary of number of unique TEAEs and patient incidence of TEAEs meeting various criteria;
- Overall summary of number of unique treatment-emergent SAEs (TESAEs) and patient incidence of TESAEs meeting various criteria;
- Patient incidence of TEAEs by MedDRA system organ class and preferred term;
- Patient incidence of the most frequently occurring TEAEs (i.e., TEAEs occurring in $\geq 10\%$ of the Safety Analysis Population) by MedDRA preferred term;
- Patient incidence of TEAEs by Common Terminology Criteria for Adverse Events (CTCAE) grade, MedDRA system organ class, and preferred term;
- Patient incidence of TEAEs by relationship to nanatinostat, MedDRA system organ class, and preferred term;
- Patient incidence of TEAEs by relationship to valganciclovir, MedDRA system organ class, and preferred term;
- Patient incidence of TEAEs by relationship to pembrolizumab, MedDRA system organ class, and preferred term;
- Patient incidence of TEAEs related to nanatinostat by CTCAE grade, MedDRA system organ class and preferred term;
- Patient incidence of TEAEs related to valganciclovir by CTCAE grade, MedDRA system organ class and preferred term;
- Patient incidence of TEAEs related to nanatinostat or valganciclovir by CTCAE grade, MedDRA system organ class and preferred term;
- Patient incidence of TEAEs related to pembrolizumab by CTCAE grade, MedDRA system organ class and preferred term;

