- Patient incidence of the most frequently occurring TEAEs related to nanatinostat (i.e., related TEAEs occurring in $\geq 10\%$ of the Safety Analysis Population) by MedDRA preferred term;
- Patient incidence of the most frequently occurring TEAEs related to valganciclovir (i.e., related TEAEs occurring in $\geq 10\%$ of the Safety Analysis Population) by MedDRA preferred term;
- Patient incidence of the most frequently occurring TEAEs related to nanatinostat or valganciclovir (i.e., related TEAEs occurring in $\geq 10\%$ of the Safety Analysis Population) by MedDRA preferred term;
- Patient incidence of the most frequently occurring TEAEs related to pembrolizumab (i.e., related TEAEs occurring in $\geq 10\%$ of the Safety Analysis Population) by MedDRA preferred term;
- Patient incidence of TEAEs leading to dosing interruption of nanatinostat by MedDRA system organ class and preferred term;
- Patient incidence of TEAEs leading to dose reduction of nanatinostat by MedDRA system organ class and preferred term;
- Patient incidence of TEAEs leading to dosing interruption of valganciclovir by MedDRA system organ class and preferred term;
- Patient incidence of TEAEs leading to dose reduction of valganciclovir by MedDRA system organ class and preferred term;
- Patient incidence of TEAEs leading to dosing interruption of nanatinostat or valganciclovir by MedDRA system organ class and preferred term;
- Patient incidence of TEAEs leading to dose reduction of nanatinostat or valganciclovir by MedDRA system organ class and preferred term;
- Patient incidence of TEAEs leading to dosing interruption of pembrolizumab by MedDRA system organ class and preferred term;
- Patient incidence of TEAEs leading to dose reduction of pembrolizumab by MedDRA system organ class and preferred term;
- Patient incidence of TEAEs related to nanatinostat leading to discontinuation of study drug by MedDRA system organ class and preferred term;
- Patient incidence of TEAEs related to valganciclovir leading to discontinuation of study drug by MedDRA system organ class and preferred term;
- Patient incidence of TEAEs related to nanatinostat or valganciclovir leading to discontinuation of study drug by MedDRA system organ class and preferred term;

- Patient incidence of TEAEs related to pembrolizumab leading to discontinuation of study drug by MedDRA system organ class and preferred term;
- Patient incidence of SAEs by MedDRA system organ class and preferred term;

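### SAP 4.6.5.4: the partial-date fallback conflicts with the prior-medication definition, so a drug known to have stopped before dosing can be tabulated as concomitant

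*SAP*

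**What the plan says.** SAP 4.6.5.4 derives the category of each medication programmatically from its start and end dates, using three statements.

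- Prior: given before first dose and "with an end date prior to date of first dose of study drug".
- Concomitant: "A concomitant medication is defined as any medication administered on or after the date of the first dose of study drug", up to 90 days after the last dose.
- Fallback: "Any medication whose start date/time cannot be determined due to partial or missing medication start and/or end dates will be considered a concomitant medication".

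The two categories are tabulated separately by cohort, and prior medications are also pooled over all patients. Each patient counts once per level (any medication, ATC class, generic name). The listing shows the phase assigned to each medication.

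The adverse event rule in SAP 4.6.2 handles incomplete dates differently. An event with a partial onset date is treatment-emergent "if it cannot be confirmed that the event onset was prior to the first dose of study drug based on the available date entries".

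On serious events, SAP 4.6.2 restricts its overall summary to treatment-emergent SAEs. Further down the same list is a table described as "Patient incidence of SAEs by MedDRA system organ class and preferred term", followed by its counterpart by CTCAE grade. Neither carries the restriction. SAP 4.6.3 calls for a listing of serious TEAEs. SAP 3.4.2.1 records adverse events from the signing of consent.

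**The concern.** The prior definition turns on the end date, whereas the fallback turns on whether the start date can be determined. The fallback therefore captures drugs whose category is already settled by a known end date. The AE rule avoids this by asking what the available date parts show; the medication rule has no such clause.

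The pattern is plausible in this trial, although the documents do not report it. Protocol 4.3 requires some drugs to be held or switched before treatment (P-gp and BCRP inhibitors, tenofovir). A long-standing drug stopped to qualify may well have an exact stop date and a vague start date. Under the fallback, a patient who complied would appear in the concomitant table as using a restricted drug on study. Protocol 5.7 treats taking an exclusionary medication on study as a deviation, and Protocol Appendix 2 links nephrotoxic and myelosuppressive co-medication to added renal and hematologic risk. A reader of the safety tables would want those rows to be right.

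The SAE labels raise a smaller issue. With collection from consent and no restriction on two tables, two programmers could produce different SAE counts, and neither need reconcile with the overall treatment-emergent summary.

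**Working it through.** The plan states no figure on this point, so there is none to reproduce. The check applies the text of SAP 4.6.5.4 to each combination of start and end dates.

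**Step 1: six date patterns.** Pre and post refer to first dose. Here a partial or missing end date is taken to say nothing about whether the drug ended before first dose. The last column is the class if a drug is concomitant unless the available dates show that it ended before first dose.

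| Start | End | Prior definition met? | Fallback applies? | Available-dates rule |
|---|---|---|---|---|
| complete, pre | complete, pre | yes | no | prior |
| partial or missing | complete, pre | **yes** | **yes** | prior |
| complete, pre | missing | no | no | concomitant |
| partial | complete, post | no | yes | concomitant |
| complete, post | missing | no | no | concomitant |
| partial | partial | no | yes | concomitant |

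Only the second pattern meets the prior definition and the fallback at once, and the SAP does not say which prevails. In the third, neither the prior definition nor the fallback applies; unless the record shows that the drug continued past first dose, it has no class. In the fifth, the concomitant definition applies directly. If a partial end date in the last row already lies wholly before first dose (for example, only a year is recorded and it is an earlier year), the case is in substance the second pattern.

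**Step 2: comparison with the AE rule.** Suppose only a calendar year is recorded, and it precedes the year of first dose. As an AE onset, that year shows that the event began before dosing, so SAP 4.6.2 does not call it treatment-emergent on onset. As a medication start, with a complete end date also before dosing, SAP 4.6.5.4 sends the drug to concomitant. The same quality of date information is used in one rule and ignored in the other.

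**Step 3: size.** Shift in a row, in percentage points = 100 × k / n, where n is the number of patients in the column and k is the number of affected patients with no other record that places them in that row. The values of k are assumptions. Cohort sizes of 3 to 6 and a Phase 1b total of 27 to 60 are the planned figures in SAP 3.1 and 4.7.

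- Cohort of 3: k = 1 gives 1/3 = 33.3; k = 2 gives 2/3 = 66.7.
- Cohort of 6: k = 1 gives 1/6 = 16.7; k = 2 gives 2/6 = 33.3.
- Pooled prior table, from which the same patient would be missing: k = 1 gives 1/27 = 3.7 down to 1/60 = 1.7.

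**Step 4: SAE labels side by side.** Treatment-emergent: the overall serious-event summary (4.6.2) and the serious-event listing (4.6.3). Not so labelled: the incidence table by system organ class and preferred term, and the one by CTCAE grade (both 4.6.2). TESAE is already a defined abbreviation in SAP Table 1, so the label was available. No arithmetic applies; this is a difference in wording.

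**The case against.** On medications, the fallback can be read as intended only for drugs that incomplete dates leave unclassifiable. On that reading a complete pre-dose end date decides the matter and there is no conflict. Sending uncertain drugs to concomitant is also the conservative direction, as in the AE rule, and the listings keep affected records visible. This is a sensible account of the likely intent, but the sentence does not say it, and classification is by program, so the words are what will be coded. It does stand that the text leaves precedence open: the SAP does not say that the fallback overrides the prior definition.

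On serious events, a reader might infer that the SAP counts pre-treatment SAEs as on-treatment. The documents do not support that. SAP 3.4.2.1 defines an AE as arising after study treatment starts. SAP 4.6.2 opens by saying that treatment-emergent events are what is summarized, and defines them as "those AEs with onset after the first dose of study drug or existing events that worsened after the first dose during the study". Its counting rule is also written for TEAEs. A table titled SAEs does not claim that its events are on-treatment, and Protocol 9.7 itself names SAEs as a subset to summarize. What remains is inconsistent wording. The AE definition does not wholly settle it, because the same section collects events from consent.

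On impact, all results are descriptive (SAP 4.1.1), and SAP 4.8 records that the study ended after Phase 1b. Both are correct and limit the severity.

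**Conclusion.** The medication point holds as an internal conflict in SAP 4.6.5.4: one identifiable date pattern meets the prior definition and is also sent to concomitant. If the last sentence is coded literally, each affected patient with no other record in a row raises that row by 16.7 points in a cohort of 6 and 33.3 points in a cohort of 3.

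This rests on three assumptions: literal programming, at least one record with this pattern, and no other on-study use by that patient in the same row. The documents give no count of partial dates. A reader might infer that on-study use of restricted drugs is in fact overstated, or that some given share of prior drugs will move. Neither can be concluded; the text shows only that overstatement is possible.

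The SAE point is secondary: a labelling inconsistency, with no stated rule that counts pre-dose events as on-treatment.

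Severity is low. The effect is confined to descriptive safety tables. ORR, DLT counts and sample size are unaffected.

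**What to change.** In SAP 4.6.5.4, keep both definitions as they stand, including the limit of 90 days after the last dose, and change only the last sentence of the definitions to:

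*If partial or missing dates prevent classification, the medication will be considered concomitant unless the available start and end date entries show that it ended before the first dose of study drug.*

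This returns the conflicting pattern to prior and also settles a complete pre-dose start with a missing end as concomitant. The change should not replace the concomitant definition itself. Without the 90-day limit, drugs started after that window would become concomitant.

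In SAP 4.6.2, change SAEs to TESAEs in the two incidence tables (by system organ class and preferred term, and by CTCAE grade), so that they reconcile with the overall summary. List any SAEs with onset before first dose separately, so that no event is lost.

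The cost is one sentence, two label changes, one added condition in the medication program and one short listing. No new data are needed.

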4.7 Determination of Sample Size

For Phase 1b, approximately 27 to 60 patients will be enrolled for up to 13 dose escalations of nanatinostat and valganciclovir and up to 10 patients in the exploratory proof-of-concept cohort of other EBV⁺ solid tumors.

Assuming the pembrolizumab ORR in RM-NPC patients in this study will be around 25%, a sample size of 30 would provide a 95% confidence interval (CI) that excludes 10% as the lower ORR. A total of 60 patients (30 per randomized treatment group) is sufficient to provide adequate estimates of tumor response for each group and to provide initial indicators of safety and tolerability. These estimates will be utilized in planning for future studies in this patient population. The sample size of N=30 per randomized treatment group was determined from nQuery Advisor tool (www.statsols.com; Statistical Solutions, Ltd, Cork, Ireland).

4.8 Changes in the Conduct of the Study or Planned Analyses

Enrollment into Study VT3996-301 was discontinued after completion of the final Phase 1b dose level for business reasons unrelated to clinical factors or safety concerns. Patients who were receiving study drugs at the time of the study discontinuation notice continued to remain on study treatment as long as they derived clinical benefit, and they were to remain on study including and up to their final Safety Follow-Up Visit. Patients who were in the Long-Term Follow-Up period transitioned to End of Study. Reporting of serious adverse events continued per clinical study protocol Section 8.2.1.

Consequently, study conduct did not proceed to Phase 2 after the recommended Phase 2 dose of nanatinostat and valganciclovir was determined, and thus the Phase 2 study-specific analyses described in this SAP will not be performed. The study will be considered complete when all patients have completed safety follow-up assessments.

The only changes to the study conduct or planned analyses identified within the development of this SAP relative to the descriptions provided within the clinical study protocol are described below:

- Section 2 of the clinical study protocol only specified ORR as a primary efficacy endpoint for Phase 2, while ORR was added as a primary efficacy endpoint for Phase 1b in this SAP.
- Section 9.1 of the clinical study protocol states that all data will be summarized by dosing regimen, disease subtype, and overall, but data summaries by disease subtype are unnecessary since Phase 1b only enrolled patients with RM-NPC, and the study did not proceed to Phase 2.

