The treatment period will begin on Cycle 1 Day 1. Cycle 1 will be 28 days; all subsequent cycles will be 21 days. Patients will be treated until unacceptable toxicity, death, progressive disease, treatment discontinuation at the discretion of the Investigator, or withdrawal of consent (maximum treatment duration with pembrolizumab is 24 months). Patients with first evidence of progressive disease and no clinical deterioration may continue study treatment until a repeat scan within 4 to 6 weeks confirms disease progression. To account for atypical disease response to immune therapy, Investigators are encouraged to follow immune-modified Response Evaluation Criteria in Solid Tumors (iRECIST) criteria (criteria based on RECIST v 1.1 for response and progressive disease, but adapted to account for the tumor response seen with immunotherapeutic drugs as described in Appendix 3 of the clinical study protocol) for treatment decision making, including confirmation of unconfirmed progressive disease with additional imaging.

Safety Follow-Up Period

Upon discontinuation of the protocol-specified treatments, patients will enter the Follow-up period. All patients must complete a safety follow-up assessment at 30 and 90 days after receiving their last dose of study drug. All AEs for patients treated with nanatinostat, valganciclovir, and pembrolizumab and only serious AEs (SAEs) for all other patients will be collected up to and including 90 days after the last dose of study treatment or until the start of a new antineoplastic therapy, whichever occurs first. The 90-day safety follow-up assessment may coincide with the first Long-Term Follow-Up visit.

Information related to concomitant medications used to treat AEs and any anti-neoplastic therapies taken following permanent discontinuation of study treatment will be collected for 90 days after the last dose of study treatment for all patients. If a new

antineoplastic treatment is initiated before the 30-day safety evaluation, safety follow-up will occur immediately before starting the new treatment. If a patient withdraws consent after the End of Treatment (EOT) visit, but prior to the 30-day safety evaluation, safety data should be collected on the patient up to the date of consent withdrawal.

Long-Term Follow-Up Visit

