3.4 Efficacy and Safety Variables

3.4.1 *Efficacy Variables*

3.4.1.1 *Primary Efficacy Variable*

Tumor responses will be assessed by the Investigator per RECIST v1.1 using MRI or CT scan assessments. For patients receiving pembrolizumab, tumor responses will also be assessed per immunologic RECIST (iRECIST). Tumor imaging will be repeated to confirm disease progression using iRECIST.

The primary efficacy endpoint is ORR, defined as the percentage of patients with a CR or PR as assessed by RECIST v1.1 within the first 26 weeks (6 months) of treatment. The ORR will also be calculated using iRECIST for patients receiving pembrolizumab.

3.4.1.2 *Secondary Efficacy Variables*

Secondary efficacy endpoints include the following:

- Time to response (TTR) – defined as the interval from the start of study drug treatment to the date of first documented CR or PR per RECIST or iRECIST.
- Duration of response (DOR) – defined as the interval of time from the date of first observed CR or PR to the date of documented disease progression or death due to any cause, whichever occurs first. Dates of progression and censoring will be determined as described in [Section 4.5.5.2](#);
- Disease control rate (DCR) – defined as the percentage of patients having a CR, PR, or stable disease (SD) at any time during treatment;
- Progression-free survival (PFS) – defined as the interval of time from the start of study drug treatment to the date of first documented disease progression, initiation of new antineoplastic therapy, withdrawal of consent, loss to follow-up, or death due to any cause, whichever occurs first. Dates of progression and censoring will be determined as described in [Section 4.5.5.2](#); and
- Overall survival (OS) – defined as the interval of time from the start of study drug treatment to the date of death due to any cause. Patients without

documentation of death at the time of analysis will be censored at the date the patient was last known to be alive.

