4.5.4 Secondary Efficacy Endpoint Analysis Methods

Disease control rate will be analyzed using the same statistical methodologies as applied to the primary efficacy endpoint in [Section 4.5.3](#).

Duration of response, PFS, and OS will be summarized in days using Kaplan-Meier methodology. The number of patients who experienced the event of interest and the number of patients censored will be presented, as will Kaplan-Meier product limit estimates of the 25th, 50th (median), and 75th percentiles with associated CIs (where estimable) using Greenwood's formula. The range for all patients, as well as those who experience the event of interest will also be summarized. Kaplan-Meier estimates of the survival distribution function over time will be generated for all patients receiving study treatment. The PFS and OS at 12 months (56 weeks) with associated 95% CIs will also be presented.

All derived efficacy measures will also be provided in a separate listing.

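### After the discontinuation notice, the end of OS follow-up depends on whether and when a patient stopped drug, and the SAP keeps an unmodified Kaplan-Meier analysis with no sensitivity check

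*SAP*

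**What the plan says.** SAP 4.8 reports that enrolment stopped after the last Phase 1b dose level and sets out what happened to patients then in the study:

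- Patients on drug at the notice could keep taking it for as long as it was helping them. The end of their follow-up is then fixed: "they were to remain on study including and up to their final Safety Follow-Up Visit". SAP 3.1 places that visit: "All patients must complete a safety follow-up assessment at 30 and 90 days after receiving their last dose of study drug".
- Patients past that stage: "Patients who were in the Long-Term Follow-Up period transitioned to End of Study".
- Patients off drug but still within 90 days of their last dose are not named. The closing sentence, "The study will be considered complete when all patients have completed safety follow-up assessments", implies that they finish their 90 days.

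SAP 3.1 gives the reasons for stopping drug, beginning: "Patients will be treated until unacceptable toxicity, death, progressive disease".

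The OS analysis was not adapted. Under SAP 3.4.1.2, patients without "documentation of death at the time of analysis will be censored at the date the patient was last known to be alive". Under SAP 4.5.4, OS is estimated by Kaplan-Meier and "The PFS and OS at 12 months (56 weeks) with associated 95% CIs will also be presented". SAP 4.5.5.1 rules out covariate adjustment. The list in SAP 4.8 that is presented as the complete set of changes does not mention OS censoring.

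**The concern.** Kaplan-Meier treats a censored patient as having the same future risk as those still being followed. Before the notice that is plausible, because the plan was to follow everyone for survival every 12 weeks whether on drug or not. After the notice, a patient leaves the OS risk set a fixed time after stopping drug, and stopping is commonly caused by progression or toxicity. Those who remain under observation are increasingly those still benefiting.

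At stake are the OS curve and the 12-month OS rate, now reported for Phase 1b only. The SAP neither mentions the problem nor offers an analysis that would reveal it, and a confidence interval does not reflect it.

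**Working it through.** The plan states no OS rate, event count or power for OS, so there is no figure to reproduce. The check is of mechanism, then of size.

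**Inputs from the documents.** The follow-up rules above; N = 27 to 60 for Phase 1b (SAP 4.7); enrolment of about 2 years (Protocol 3.2), taken as uniform over 24 months.

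**Assumed inputs.** Notice 1 or 6 months after last entry. Median time on drug 2, 4 or 7 months, bracketed by the median PFS of 1.9 and 7.0 months quoted for other regimens in Protocol 1.2.1. Median survival 24 to 48 months at the on-drug death rate and 8 to 12 months at the off-drug rate.

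**1. The rule as a formula.** If safety-window patients finish their 90 days, OS follow-up ends at the later of (notice date) and (last dose + 90 days). For a patient in long-term follow-up this is the notice. For a patient on drug it is set by the date of stopping.

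**2. Direction.** At time t the estimated hazard is w × h_on + (1 − w) × h_off, where w is the share of the risk set still on drug and each hazard is ln 2 / median. For medians of 48 and 8 months:

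- h_on = 0.693/48 = 0.0144 per month
- h_off = 0.693/8 = 0.0866 per month, six times higher

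In person-time after the notice, patients more than 90 days off drug are missing, so w is too large.

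- h_off > h_on: estimated hazard too low, OS too high.
- h_off = h_on: w cancels, no bias.
- h_off < h_on, or off-drug risk highest in the first 90 days (the only off-drug time retained): OS can be too low.

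**3. Size, pooled, constant and higher off-drug hazard.** Simulation with 1.5 million patients per scenario, Kaplan-Meier minus true OS. The table is for the strictest reading, in which everyone off drug is cut at the notice.

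| Time | Bias (points) |
|---|---|
| 12 months | +0.1 to +2.3 |
| 56 weeks (56 × 7 / 30.44 = 12.9 months) | +0.1 to +2.7 |
| 18 months | +0.1 to +5.0 |
| 24 months | 0 to +8.3 |

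One scenario in full (notice 6 months after last entry, median 7 months on drug, medians 48 and 8):

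| Months | True OS | SAP rule | Bias | Share of risk set observed after the notice |
|---|---|---|---|---|
| 12 | 61.5% | 62.3% | +0.7 | 15% |
| 18 | 42.7% | 45.0% | +2.3 | 28% |
| 24 | 28.5% | 32.6% | +4.1 | 47% |

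Bias is taken before rounding. It grows with time because a growing part of the risk set is observed after the notice; person-time before the notice is unaffected. If safety-window patients finish their 90 days, the bias is generally of similar size or somewhat smaller when the notice comes soon after last entry. If off-drug risk rises after the first 90 days, the bias at 24 months reaches +10.7.

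**4. Other hazard patterns, at 24 months.**

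- Equal hazards: 0.
- Off-drug deaths concentrated in the first 90 days (median 4 months, then 16): −1.8 to +0.2, or −2.5 to −0.7 if safety-window patients finish.
- Higher risk on drug (medians 12 on, 24 off): −0.4 to −3.3.

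**5. Against sampling error.** In one scenario (medians 48 and 12, 4 months on drug) the standard deviation of the 12-month estimate was about 7 points at N = 60 and 10 at N = 27. The pooled 12-month bias is smaller than either.

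**6. Late cohorts.** Dose levels enrolled in sequence, so the last ones have the most person-time after the notice. For patients entering 1 to 6 or 2 to 9 months before it, with off-drug risk higher and safety-window patients finishing, the overstatement was about 4 to 10 points at 12 months and 6 to 15 at 18 months. The weakest contrast (24 versus 12 months) lies at or slightly below the bottom of these ranges.

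**7. Common cut-off at the notice.** With vital status known on that date, bias was within 0.1 point in every pooled scenario, because censoring then depends only on entry date. For cohorts that all entered within 9 months of the notice, 12-month OS is not estimable this way.

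**The case against.** The case against acting has real weight.

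- **Precision and use.** OS is secondary, descriptive and not compared between regimens (SAP 4.1.1, 4.5.5.5). Cohorts are of 3 to 6 patients; even a fully observed 3 of 6 has an exact 95% interval of 12% to 88%. Survival follow-up ending on sponsor termination was foreseen (SAP 3.1), and the change in conduct is disclosed. This stands, and it sets the priority. It does not remove the bias, and an end that differs by treatment status was not foreseen.
- **The remedy is not clean.** Off-drug patients are contacted every 12 weeks, and no final survival contact at the notice is described. If deaths are known up to the notice but off-drug survivors are censored at their last contact, the common cut-off gives −0.5 to −1.8 points at 12 months: similar in size, opposite in sign. This stands. The contact gap also affects the current rule, and it argues for showing both analyses.

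Three stronger readings are tempting, and the documents do not support them. A reader might infer that everyone off drug left at once, but SAP 4.8 says this only of long-term follow-up patients. A reader might infer that OS is certainly biased upward, but the sign depends on hazards that the documents do not give. A reader who assumes 12-month accrual could obtain 3 to 9 points for pooled 12-month OS, but Protocol 3.2 anticipates about two years.

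**Conclusion.** The point holds. For person-time after the notice, OS censoring is linked to stopping drug, independent censoring fails, and the SAP does not address it. Upward bias is the likelier direction if death risk rises after stopping, but that is an inference.

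Pooled, the size is about 0 to 2 points at 12 months and 0 to 5 at 18 months, less than sampling error at 12 months. In the last-enrolled cohorts it can be about 4 to 10 points at 12 months, so estimates by regimen could flatter the last dose levels tested.

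These figures rest on assumed hazards, time on drug and notice date. The two-year enrolment is also a forecast for the whole study: if Phase 1b accrued faster, the pooled figure moves toward the late-cohort one. The documents do not give the number on drug at the notice. This is a worthwhile but optional improvement.

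**What to change.** In SAP 3.4.1.2 and 4.5.4:

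1. State the date of the discontinuation notice.
2. Add an OS analysis, at least as a sensitivity analysis, with a common cut-off on that date for every patient. Censor those alive at the notice if vital status is known then; otherwise apply one contact rule to both deaths and alive dates. List later deaths without counting them.
3. Present it beside the version censored at last known alive.
4. State how patients inside the 90-day safety window at the notice are handled.
5. Report censoring counts by reason: notice, end of safety follow-up, loss to follow-up, withdrawal.
6. Do not report 12-month OS for cohorts where the common cut-off leaves it not estimable.

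The cost is SAP wording and one extra table. The downside is that some late deaths and follow-up time are left out of the added estimate, and some late cohorts will have no 12-month figure from it.
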